This is an exploratory vaccine trial to evaluate immunogenicity of a non-licensed dosing schedule and route of administration for a currently FDA licensed rabies vaccine for pre-exposure prophylaxis against rabies infection. The goal of this study is to characterize the immune response and persistence of immunity to a shortened dose schedule and intradermal (ID) administration, relative to the current licensed dosing schedule of the rabies vaccine (3 dose (0, 7, 21 days) IM). Rabies virus is endemic throughout the world due to high rates of both wild and domestic animal rabies and the risk to deployed military in endemic areas is considerable. Currently the commonly supported pre-exposure prophylaxis regimen for rabies, in the United States is comprised of three, 1.0 ml intramuscular (IM) injections of the human diploid cell vaccine (HDCV) or purified chick embryo cell (PCEC) rabies vaccine on days 0, 7, and 21 or 28. Modified, two and three dose schedules of intradermal (ID) injections of 0.1 ml of HDCV and PCEC are the standard outside the US. These two and three dose intradermal schedules share a similar safety and immunogenicity profile to intramuscular vaccinations and are easily boosted at one year after vaccination. A death, this year, from rabies, of a US Soldier returned from Afghanistan underscores the importance of rabies pre-exposure prophylaxis for soldiers and the need to evaluate the safest, most effective means of vaccinating large deploying forces. While the current three dose, 1 ml IM rabies series is effective, a shortened, equally effective vaccination series with significantly smaller dose per injection would greatly improve the logistics and cost associated with universal or even targeted coverage of deploying soldiers. Evaluation of a shorter, smaller-dose, pre-exposure vaccination series for rabies is the goal of this study.

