An administrative amendment to a protocol is one that modifies some administrative or logistical aspect of the trial but does not affect its design or objectives or have an impact on the subjects' safety. Regulatory authorities need only be notified about administrative changes. Sites will be required to submit any administrative amendments to their IRB for notification and/or approval. The Investigator is responsible for ensuring that changes to an approved trial, during the period for which IRB approval has already been given, are not initiated without IRB review and approval, except to eliminate apparent immediate hazards to subjects.

9 Vaccines Administered

Subjects in Group 1 will receive 3 doses of Rabies vaccine administered IM at Days 0, 7,21 and 365.

Subjects in Group 2 will receive 3 doses of Rabies vaccine administered ID at Days 0, 7,21 and IM at Day 365.

Subjects in Group 3 will receive 2 doses of Rabies vaccine administered IM at Days 0,7 and 365.

Subjects in Group 4 will receive 2 doses of Rabies vaccine administered ID at Days 0,7, and IM at Day 365.

Subjects in Group 5 will receive 1 dose of Human Serum Albumin administered IM at Day 0.

Subjects in Group 6 will receive 1 dose of Human Serum Albumin administered ID at Day 0.

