Exploratory statistical analyses of final data may be conducted, if indicated by the descriptive results. Parametric, non-parametric and resampling (bootstrapping) methods for statistical inference may be used in exploratory analyses, based on data compliance with assumptions of methods. P -values ≤ 0.05 will be considered significant and p-values ≤ 0.10 will be considered a trend. Confidence intervals will be constructed at $\alpha=0.05$ and $\alpha=0.10$. When necessary, p-value corrections for multiple comparisons will be applied.

A descriptive summary of adverse events that were reported throughout the trial will be produced.

Descriptive and inferential analyses (if any) will be carried out using SAS Version 9.2 (or more recent versions), which is licensed and supplied by SAS Institute, Cary, NC, USA.

Per-Protocol Analysis Set

The Per-Protocol (PP) analysis set will include all subjects who had no protocol deviations at the time that the data was collected. Three PP analysis sets will be produced for the primary objective that will contain separate data from blood drawn on day 0, day 28 and day 372, respectively. Descriptive analysis of the secondary endpoint will require a fourth per protocol analysis set for blood drawn on day 365. Subjects will be excluded from the PPAS for the following reasons:

1. Subject did not meet all protocol-specified inclusion/exclusion criteria or definitive contraindications (only for the second and third vaccination)
2. Subject did not receive the correct number of injections
3. Administration of vaccine was not done as per protocol (site and route of administration)
4. Subject did not receive vaccine in the proper time window defined in the tables of the study procedures
5. Subject did not provide a post-dose serology sample in the proper time window defined in the tables of the study procedures

Subjects will remain in this population as long as they do not meet one of the above criteria, except for blood sampling timing and validity of the serology test result*. A PP set will be defined for each injection.

***Note:** For example, a subject whose time period is outside the defined visit window only between the first injection and the blood sample taken after the first injection will be excluded from PP1 but may be kept in PP2 or PP3.

Subjects will be analyzed by the vaccine group to which they were randomized, subject to the exclusion criteria above

Full Analysis Set

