Timepoints: At baseline, 28 days and 372 days.

- Number and percentage of subjects with a titer ≥ 0.5 IU/ml against rabies virus by treatment group at days 0, 28 and 372.

A table that presents the total number of per-protocol subjects and the number and percent of each treatment group who have a titer ≥ 0.5 IU/ml against rabies virus at days 0, 28 and 372 will be produced.

Statistical Methods for Secondary Immunogenicity Objectives

Immunogenicity will be assessed descriptively using the following parameters:

Timepoints: Days 0, 28 and 365.

A table that presents, by treatment group, the total number of per protocol subjects and the number and percent of each group who have IgG titers ≥ 0.5 IU/ml against rabies virus at days 0, 28 and 365 will be produced.

Statistical Methods for Adverse Events and Serious Adverse Events

For each treatment group, a line listing by subject that describes adverse events and post-baseline day of occurrence of the AE will be produced.

The number and percent of subjects in each group who reported any AE between Days 0 and 372 will be summarized in tabular format.

A table showing the number and percentage of subjects in each group who reported adverse events by general type (category) of event will be produced.

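### The any-AE table pools Days 0–372, so the ID-primed groups' percentages include AEs after the IM boost, and no summary table separates priming from boost

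*SAP*

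**What the plan says.** The SAP section on adverse events plans three outputs.

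- An any-AE table: "The number and percent of subjects in each group who reported any AE between Days 0 and 372 will be summarized in tabular format".
- Counts by AE category, namely the "number and percentage of subjects in each group who reported adverse events by general type (category) of event", with no time window stated.
- Listings within every arm: "a line listing by subject that describes adverse events and post-baseline day of occurrence of the AE will be produced".

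In its general Statistical Methods text, the SAP adds: "A descriptive summary of adverse events that were reported throughout the trial will be produced".

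Protocol section 9 sets the doses. For the three-dose IM group: "Subjects in Group 1 will receive 3 doses of Rabies vaccine administered IM at Days 0, 7,21 and 365". For its ID counterpart: "Subjects in Group 2 will receive 3 doses of Rabies vaccine administered ID at Days 0, 7,21 and IM at Day 365". Groups 3 and 4 follow the same pattern without the Day 21 dose, and Group 4 also switches to IM at Day 365. The boost is therefore IM in all four vaccine groups.

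**The concern.** The groups differ in priming route (ID or IM) and in number of priming doses (two or three). After that they converge on the same IM injection a year later. A percentage that counts each subject once over the whole period combines three things: AEs after priming, where the groups differ; AEs during a long gap without doses; and AEs after a boost that is identical in every vaccine group. One of the four injections in Group 2, and one of the three in Group 4, is by the other route.

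At stake is how the by-group AE percentages will be read. The Protocol's Introduction motivates the trial by the "need to evaluate the safest, most effective means of vaccinating large deploying forces", and readers will naturally set the ID and IM columns side by side. The added components are common to all vaccine arms, so they pull the columns together. Titers are tabulated separately before and after the boost; AEs are not.

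The point concerns Groups 1 to 4 only. The control groups leave after Day 7, which is a separate comparability matter.

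**Working it through.** **The plan's own figures.** The only design figure is the sample size: 4 × 12 + 2 × 6 = 60, which agrees with the allocation. No AE rate by route, boost or background is given, so there is no safety figure to reproduce.

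**Dose-free gap (Protocol section 9).**
- Groups 1 and 2: 365 − 21 = 344 days, which is 344/372 = 92.5% of the table window.
- Groups 3 and 4: 365 − 7 = 358 days, which is 358/372 = 96.2%.
- With the visit windows (±1 day for these priming doses, ±15 for the boost), the gap can be 328 to 360 days and 342 to 374 days.

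**End of the window (study procedure tables).** With ±15 days, the boost can fall as late as 365 + 15 = Day 380 and the final visit as late as 372 + 15 = Day 387. A literal Day 372 cut-off can therefore omit post-boost AEs.

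**Attenuation.** Let p be the risk of any AE during priming, q the risk after the IM boost, and b the risk in the dose-free interval. Assume q and b are the same in both routes and independent of p. Then:

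P(any AE) = 1 − (1 − p)(1 − q)(1 − b)

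pooled route difference = (p_IM − p_ID)(1 − q)(1 − b)

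The multiplier equals 1 only if neither the boost nor the interval produces an AE.

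**Illustration, with all rates assumed.** For k priming doses with per-dose risk r, p = 1 − (1 − r)^k, and q is the IM per-dose risk. Here b = 0.

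| Assumed per-dose risk | Contrast | Priming only | With IM boost |
|---|---|---|---|
| IM 30%, ID 10% | Group 1 v 2 | 1 − 0.7³ = 65.7% v 1 − 0.9³ = 27.1%; 38.6 points | 1 − 0.7⁴ = 76.0% v 1 − 0.9³ × 0.7 = 49.0%; 27.0 points |
| IM 30%, ID 10% | Group 3 v 4 | 51.0% v 19.0%; 32.0 points | 65.7% v 43.3%; 22.4 points |
| IM 10%, ID 30% | Group 1 v 2 | 27.1% v 65.7%; 38.6 points | 1 − 0.9⁴ = 34.4% v 1 − 0.7³ × 0.9 = 69.1%; 34.7 points |
| IM 10%, ID 30% | Group 3 v 4 | 19.0% v 51.0%; 32.0 points | 27.1% v 55.9%; 28.8 points |

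**Adding interval AEs.** With b assumed at 30% or 60%, multiply the last column by 0.7 or 0.4:
- IM 30%, ID 10%: Group 1 v 2 becomes 18.9 or 10.8 points; Group 3 v 4 becomes 15.7 or 9.0.
- Reversed: Group 1 v 2 becomes 24.3 or 13.9 points; Group 3 v 4 becomes 20.2 or 11.5.

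**Scale.** One subject in an arm of 12 is 100/12 = 8.3 points. The boost alone moves the Group 1 v 2 gap by (38.6 − 27.0)/8.3 = 1.4 subjects in the first scenario and (38.6 − 34.7)/8.3 = 0.5 in the reversed one.

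**What is collected.** Protocol section 5 names unsolicited AEs within 30 minutes of a dose, with SAEs recorded throughout. The study procedure tables and section 5.3 call for AE and SAE assessment at follow-up visits. On the first reading, b covers serious events only. On the second, b includes ordinary illness, although Day 77 is the only scheduled visit between Day 28 and Day 365. The boost component arises on either reading, because section 16.3.1 requires observation after every rabies vaccination.

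**The case against.** The strongest reply is that no route safety contrast is planned. Every stated objective is an immunogenicity objective, and the SAP excludes formal hypothesis tests. The Introduction's remark about safety is motivation, and the same section says that ID and IM schedules have similar safety profiles, in which case there is little to dilute. The first part stands and limits the priority. The second is a premise rather than a result of this trial, and a table that draws the groups together cannot help a reader judge it.

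It can also be said that the IM boost is part of the regimen to which Groups 2 and 4 are randomized, so counting a post-boost AE there is a correct summary by regimen. That stands too. The whole-study total is valid for that question, but it does not describe the safety of the priming route.

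A reader might infer that the pooling conceals a route difference. The documents do not support that: the listing gives each AE's day of onset, and with 12 subjects per vaccine arm the periods can be separated by hand. The loss is in the summary tables, not in the data.

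A reader might also infer that both tables are fixed to Days 0–372. Only the any-AE table states that window; for the category table, pooling is inferred from the SAP's general sentence on AEs. Tabulation by type may separate injection-site reactions from ordinary illness, but it does not separate boost from priming.

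**Conclusion.** The point holds as a weakness of presentation. The only AE percentage with a stated window combines priming, a gap of 344 or 358 days and a common IM boost, and no planned summary separates them. That an absolute route difference shrinks follows if boost and interval risks are equal across routes and independent of priming AEs. If subjects who report one AE are prone to report others, the multiplier would differ.

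The size is hypothetical, since every AE rate above is assumed. It would be tempting to conclude that the pooling masks a difference equally in either direction. The arithmetic does not bear this out: if ID is the more reactogenic route, the boost alone takes the Group 1 v 2 gap only from 39 to 35 points. The interval's contribution cannot be sized until the AE collection passages agree. Priority is modest.

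**What to change.** Present both AE tables by period, using each subject's actual dose and visit dates:

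- **Priming:** first dose to the Day 28 visit.
- **Interval:** after the Day 28 visit to before the boost.
- **Post-boost:** the boost to the final visit, even if that falls after Day 372.

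State the denominator for each period (for post-boost, subjects given the boost) and a rule for AEs with onset on the boost day, since the listing gives a day and not a time. Describe safety by route and number of doses from the priming period, and keep the whole-study total as a supplement.

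Separately, reconcile Protocol section 5 with the study procedure tables and section 5.3 on whether non-serious AEs are collected beyond 30 minutes after a dose, and say in the SAP which AEs the tables count.

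The cost is SAP wording and extra table panels. No new data are needed: onset days are already to be listed, and dose and sample dates are needed anyway to apply the per-protocol window criteria.
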